#### 4.5.2. Tertiary Patient Reported Outcome

# 4.5.2.1. Basal Insulin Experience: Likelihood of Incorporating Into Routine

This is a Lilly-developed, participant-completed question to understand the participant's likelihood of incorporating their study insulin into their diabetes management routine. The question is rated on a 5-point scale with responses ranging from "very unlikely" to "very likely."

The frequency and proportion of the responses at Week 52 (Visit 33) will be summarized by study treatment. Wilcoxon rank sum test will be used for treatment comparison. In addition, the last non-missing postbaseline observations prior to or at the time of switch to LY3209590 with a prefilled pen will be summarized and compared to the last non-missing postbaseline observations for insulin glargine by Wilcoxon rank sum test.

#### 4.5.3. Other Efficacy Endpoints

- Participants will perform SMBG 6-point profiles over a 24-hour period on 2 nonconsecutive days during the 7-day period prior to visits shown in the SoA of the protocol. The 6-point profile consists of pre-meal and 2-hour postprandial SMBG measurements for the morning, midday, and evening meals during 1 day. The following SMBG variables will be analyzed and summarized based on the EAS2 data. Only participants with an observation at baseline or at the postbaseline visits will be included in the analysis. The missing baseline and postbaseline visits will be imputed using multiple imputation under assumption of missing at random. MMRM analysis will be conducted similar to that for the primary endpoint with an additional term of baseline HbA1c stratum (<8.0%, ≥8.0%). The statistical inference will be based on the multiple imputation framework by Rubin (1987).Between-day GV measured by the CV and SD of the FBG by SMBG
- Average of the SMBG values at each time point from 6-point SMBG profiles (pre-meal and 2-hour postprandial SMBG measurements for the morning, midday, and evening meals) collected during the 7-day period prior to visits
- Within-day and between-day GV measured by the CV and SD of 6-point SMBG. The between-day GV from SMBG was calculated in 2 steps: (1) GV at each time point calculated from values collected during the 7-day period prior to visits; (2) between-day GV calculated by averaging GVs over SMBG time points

#### 4.5.4. Tertiary Safety Endpoints

For tertiary safety measures, the details are provided in Section 4.6 and the following subsections.

### 4.6.1. Extent of Exposure

Duration of exposure to study treatment will be summarized. No p-values will be reported in these tables as they are intended to describe the study populations, rather than test hypotheses about them. Total patient-years of exposure will be reported. The number and proportion of participants falling into the following different exposure categories will also be summarized by study treatment

- $>0, \ge 30 \text{ days}, \ge 90 \text{ days}, \ge 180 \text{ days}, \ge 365 \text{ days}$
- >0 and <30 days, ≥30 and <90 days, ≥90 and <180 days, ≥180 and <365 days

Exposure on study treatment will be calculated as

- LY3209590: date of the last treatment administration date of first treatment administration + 7 days
- Insulin glargine: date of the last treatment administration date of first treatment administration + 1 day

Total patient-years of exposure will be calculated by the sum of duration of exposure in days divided by 365.25. The following summary statistics will be provided: n, mean, standard deviation, median, minimum, maximum, interquartile range, and total exposure (that is, total patient-years).

All participants who complete the study treatment period are required to complete a safety follow-up period and participants who discontinue the study treatment prematurely are encouraged to remain in the study for safety monitoring. The duration on study from the first dose of study treatment to the final study disposition date will also be summarized by treatment.

A listing of exposure to study treatment will be provided.

#### 4.6.2. Adverse Events

Events that are newly reported after the first dose of IP or reported to worsen in severity from baseline will be considered TEAEs. The MedDRA LLT will be used in the treatment-emergent assessment. The maximum severity for each LLT during the baseline period (see the table in Section 4.1) will be used as baseline severity.

The table below describes the analysis related to AEs.

Analysis	Details	
Overview of AEs	Number and percentage of participants who experienced:	
	• SAE	
	Death	
	Discontinuation from study treatment due to an AE	
	Discontinuation from study due to an AE	
	• TEAE	
	TEAE related to study treatment	
Summary by PT within System	Number and percentage of participants with TEAEs using MedDRA PT nested	
Organ Class (SOC)	within SOC:	
	• TEAE	
	Maximum Severity TEAEs	
	• SAE	
	AE leading to permanent discontinuation of study treatment	
	Events will be ordered by decreasing risk difference within. SOCs will be	
	listed by decreasing risk difference.	
	For each participant and TEAE, the maximum severity for the MedDRA PT is	
	the maximum postbaseline severity observed from all associated LLTs	
	mapping to the MedDRA PT. The maximum severity will be determined based	
G 1 PT ( :d: G) (O	on the non-missing severities.	
Summary by PT (within SMQ	Number and percentage of participants with TEAEs using MedDRA PT	
when applicable)	(irrespective of SOC):	
	• TEAEs (occurring in ≥1% before rounding in LY3209590 group)	
	TEAE of safety topic of interest by PT (within SMQ when	
	applicable)	
Listing	Events will be ordered by decreasing risk difference.  Separate listings for the following AEs or events will be provided:	
Listing	SAE including death	
	AEs leading to study treatment discontinuation	
	Severe hypoglycemia	
	Events sent to the external adjudicator for MACE adjudication	
	Participants who receive rescue therapy due to severe/persistent	
	hyperglycemia	
	Persistent-recurrent hypoglycemia reported by investigators	
	Persistent recurrent hypoglycemia identified by programing	
	Medication errors of interest	
	TITE 1 1 1 1 1 NACE 1 1 1 1	

Abbreviations: AE = adverse event; LLT = lowest level term; MACE = major adverse cardiovascular event; MedDRA = Medical Dictionary for Regulatory Activities; SAE = serious adverse event; SOC = System Organ Class; PT = preferred term; TEAE = treatment-emergent adverse event.

#### 4.6.2.1. Safety Topics of Interest

#### 4.6.2.1.1. Severe Hypoglycemia

Severe hypoglycemia: A severe event characterized by altered mental and/or physical status requiring assistance for treatment of hypoglycemia. The determination of a hypoglycemic event as an episode of severe hypoglycemia is made by the investigator based on the medical need of the participant to have required assistance and is not predicated on the report of a participant

simply having received assistance. If a hypoglycemic event meets the criteria of severe hypoglycemia, the investigator must record the event as serious on the AE CRF.

A summary of severe hypoglycemia by decreasing risk difference will be provided. The incidence and event rate during the treatment period will be analyzed using the method described in Section 4.6.3.1. A listing of severe hypoglycemia events will also be provided.

#### 4.6.2.1.2. Persistent-Recurrent Hypoglycemia

The potential risk of persistent-recurrent hypoglycemia (P-R hypoglycemia) will be assessed from the first dose date up to the end of the study and will be based on two approaches to identify persistent-recurrent hypoglycemic events:

- 1. using investigator assessment and clinical judgment to determine if repeated hypoglycemia may have contributed to a hypoglycemic event that degenerated with poor outcomes, and
- 2. using a prespecified criteria to derive events from e-diary database (see definition in Appendix 10 (Section 6.9).

Identification of P-R hypoglycemia based on investigator reporting is precipitated by a hypoglycemic event a participant or their caregiver inform having resulted in a poor outcome. This information will trigger an e-mail alert notifying the investigator to contact the study participant, obtain more information about the specific hypoglycemic event, and provide them clinical guidance, if appropriate. Hypoglycemic events that trigger alerts to investigators are those participants or caregivers report in the e-Diary have required treatment with glucagon or IV glucose, resulted in coma, motor vehicle accident or other trauma, hospitalization, or emergency medical care.

Upon receiving the e-mail notification, investigator will access the e-Diary database and answer the following question: "In your clinical judgement, is this hypoglycemia event associated with repeated hypoglycemia events?". Investigator should select "Yes" or "No" as an answer.

During protocol training, investigators are trained to consult the e-Diary database and review participant's blood glucose values and hypoglycemia reports to determine the best answer. If investigator judges the hypoglycemic event that triggered an alert is related to repeated episodes of hypoglycemia, the participant will be identified as having presented a P-R hypoglycemic event reported by the investigator.

P-R hypoglycemia events and participants who present P-R hypoglycemia will be identified by one or both approaches explained above. Summary statistics and a listing of the events identified by both methods will be provided.

#### 4.6.2.1.3. Systemic Hypersensitivity Reactions

Hypersensitivity reactions are exaggerated or inappropriate immunologic responses occurring in response to an antigen or allergen. These can be systemic or localized. At all visits, participants will be evaluated by the investigator for signs and symptoms suggestive of hypersensitivity. Investigators will complete a CRF designed to record additional information about AEs suggestive of a hypersensitivity reaction. Analyses are based on the following:

• Anaphylactic reaction SMQ (20000021; narrow terms)

- Hypersensitivity SMQ (20000214; narrow terms)
- Angioedema SMQ (20000024; narrow terms)

The number and percentage of participants reported with a TEAE for the following will be analyzed:

- Any narrow term from any 1 of the 3 SMQs indicated above (that is, combined search across narrow portions of all 3 SMQs)
- Any narrow term within each SMQ, separately (that is, narrow SMQ search)

Individual PTs that satisfied the query will appear in the summary in decreasing order of risk difference between LY3209590 and insulin glargine group.

The analyses above are the starting point for medical interpretation of any apparent differences between treatment groups. For notable events, case review will be applied to make the final determination of whether an event is most accurately described as a potential hypersensitivity reaction to study treatment, or another event that is not clearly associated with study treatment administration. This judgment will be on the basis of totality of information available, including the content of a follow-up CRF collected for potential hypersensitivity events.

#### 4.6.2.1.4. Injection Site Reactions

ISRs are AEs localized to the immediate site of the administration of a medication. The evaluation of ISRs will be through the unsolicited reporting of ISR TEAEs and through the use of an Injection Site Reaction Follow-up Form completed by the investigator for each incidence of ISR. A summary of the number of participants with reported events meeting any of the following categories will be provided:

- MedDRA HLT of Injection site reactions
- MedDRA HLT of Administration site reactions
- Lipodystrophies and localized amyloidosis, as represented by PTs of:
  - Lipoatrophy
  - o Lipodystrophy acquired
  - o Partial lipodystrophy
  - Lipohypertrophy
  - o Sclerema
  - o Cutaneous amyloidosis

#### The summary will present

- The number of participants reported at least one AE meeting any of the above categories
- The number of participants reported any AE in each category
- The number of participants reported any AE for each PT within a specific category

The PTs will be listed for summary within each category in decreasing risk difference between LY3209590 and insulin glargine group.

The additional data collected on the ISR follow-up forms will be summarized in 2 distinct ways:

1. at the participant-level (each participant contributes to totals at most once, regardless of the number of ISR events the participant experienced), and

2. at the event level (each separate event contributes to totals, regardless of whether the participant experienced multiple ISR events).

#### 4.6.2.1.5. Neoplasms

The TEAEs of neoplasms will be identified by narrow search for the following SMQ:

- Malignant tumours SMQ (20000194, narrow terms)
- Tumours of unspecified malignancy SMQ (20000195, narrow terms)

#### A summary will presented

- Any narrow term from any 1 of the 2 SMQs indicated above (that is, combined search across narrow portions of both SMQs)
- Any narrow term within each SMQ, separately (that is, narrow SMQ search)

#### 4.6.2.1.6. Diabetic Ketoacidosis (DKA)

The DKA will be searched by MedDRA PTs from all TEAEs. The number and percentage of participants experiencing treatment-emergent DKA will be summarized. The TEAEs of DKA will be identified using MedDRA PTs of

- Diabetic ketoacidosis
- Ketoacidosis
- Euglycaemic diabetic ketoacidosis
- Ketonuria
- Diabetic ketosis
- Diabetic ketoacidotic hyperglycaemic coma
- Ketosis
- Urine ketone body present
- Blood ketone body
- Blood ketone body increased
- Urine ketone body
- Blood ketone body present
- Lactic acidosis

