#### 4.6.2.1.8. Peripheral Edema

The peripheral edema will be searched by MedDRA PTs (see Section 6.7) from all TEAEs. The number and percentage of participants experiencing treatment-emergent peripheral edema will be summarized by PT.

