# 6.7. Appendix 7: MedDRA PT for Peripheral Edema

The analysis of peripheral edema (Section 4.6.2.1.8) will be based on the TEAEs in the following terms:

- Acute pulmonary oedema
- Ascites
- Brain oedema
- Bronchial oedema
- Capillary leak syndrome
- Cerebral oedema management
- Compression garment application
- Cytotoxic oedema
- Effusion
- Fluid retention
- Gastrointestinal oedema
- Generalised oedema
- Gravitational oedema
- Hydraemia
- Hypervolaemia
- Hypoosmolar state
- Lipoedema
- Lymphoedema
- Negative pressure pulmonary oedema
- Non-cardiogenic pulmonary oedema

- Non-pitting oedema
- Oedema
- Oedema blister
- Oedema due to cardiac disease
- Oedema due to hepatic disease
- Oedema due to renal disease
- Oedema mucosal
- Oedema peripheral
- Pelvic fluid collection
- Pericardial effusion
- Perinephric collection
- Perinephric oedema
- Peripheral swelling
- Pleural effusion
- Pulmonary oedema
- Retroperitoneal effusion
- Retroperitoneal oedema
- Skin oedema
- Skin swelling
- Subdural effusion
- Swelling
- Visceral oedema

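### The SAP's pooled count of treatment-emergent DKA takes in ketosis, ketone-test and lactic acidosis terms, so as labelled it is not an incidence of DKA; the peripheral edema list has a milder labelling problem

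*SAP*

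**What the plan says.** SAP 4.6.2.1.6 sets both the summary and the case definition for this safety topic: "The number and percentage of participants experiencing treatment-emergent DKA will be summarized. The TEAEs of DKA will be identified using MedDRA PTs of". The list that follows has 13 entries. Among them are "Lactic acidosis" and "Urine ketone body present". The section specifies one pooled count, with no narrower tier and no case review.

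SAP 4.6.2.1.8 treats edema differently. There the "number and percentage of participants experiencing treatment-emergent peripheral edema will be summarized by PT", using the terms in Appendix 7 (SAP 6.7). That appendix has 42 entries under the peripheral edema title, running from "Acute pulmonary oedema" to skin terms and including "Subdural effusion".

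Two general provisions in the SAP 4.6.2 table also apply. TEAEs belonging to a safety topic of interest are tabulated by PT, and all serious adverse events are listed. Under SAP 4.6, percentages use the mITT population as denominator.

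**The concern.** DKA is a specific diagnosis. A table row carrying that name will be read as the proportion of participants who had it. Under the rule as written, a participant with only ketonuria, a ketone laboratory term or lactic acidosis is counted in that row. Two of the ketone terms (*Blood ketone body* and *Urine ketone body*) do not even state an abnormal result.

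Other topics in the same part of the SAP are more careful:

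- Hypersensitivity (4.6.2.1.3) uses narrow SMQ terms, shown combined and separately, with case review of notable events.
- Neoplasms (4.6.2.1.5) uses narrow terms, shown combined and separately.
- Hypokalemia (4.6.2.1.9) uses narrow terms only.
- MACE (4.6.2.1.11) counts only events confirmed by adjudication.
- The hepatic search (4.6.3.2) is broad, but its label presents the yield as potential cases.

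The DKA topic joins a broad search to a diagnostic label and has none of these safeguards. At stake is the accuracy of one named safety incidence by arm. If counts are low, a few off-target reports could produce an apparent imbalance in that row or dilute a real one.

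**Working it through.** The documents state no expected rate, power or decision rule for DKA or edema, so there is no planned figure to reproduce. The check is a count and classification of the listed terms by their wording, followed by an illustration.

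**DKA list (SAP 4.6.2.1.6)**

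| Group | Terms | Count |
|---|---|---|
| Names ketoacidosis | Diabetic ketoacidosis; Ketoacidosis; Euglycaemic diabetic ketoacidosis; Diabetic ketoacidotic hyperglycaemic coma | 4 |
| Ketosis | Diabetic ketosis; Ketosis | 2 |
| Ketonuria | Ketonuria | 1 |
| Ketone test terms | three blood and two urine ketone body terms | 5 |
| Other condition | Lactic acidosis | 1 |

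Total: 4 + 2 + 1 + 5 + 1 = 13. Terms that do not name ketoacidosis: 13 − 4 = 9, and 9/13 = 69%. This is a share of dictionary terms, not of events.

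**Can the by-PT rows recover the DKA incidence?** Not in general. One participant can appear under more than one PT. If two ketoacidosis rows each show 2 participants, the number of distinct participants lies anywhere from 2 (complete overlap) to 2 + 2 = 4 (none). A count of distinct participants over the 4 terms has to be specified.

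**Illustration.** Planned size is 670 randomized 1:1 (SAP 5), so 670/2 = 335 per arm. The mITT denominator may be slightly smaller. The event counts below are assumptions.

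Reported percentage = (true cases + participants with only off-target terms) / 335.

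| True DKA | Off-target only | True % | Reported % |
|---|---|---|---|
| 0 | 1 | 0.0 | 1/335 = 0.3 |
| 1 | 1 | 0.3 | 2/335 = 0.6 |
| 1 | 3 | 0.3 | 4/335 = 1.2 |
| 1 | 5 | 0.3 | 6/335 = 1.8 |

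**Edema list (SAP 6.7)**

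The list has 42 terms. Organ oedema or cavity fluid accounts for 19:

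- Lung and airway, 5: acute pulmonary, pulmonary, negative pressure pulmonary, non-cardiogenic pulmonary, bronchial.
- Brain and subdural, 4: brain oedema, cerebral oedema management, cytotoxic oedema, subdural effusion.
- Chest and abdominal or pelvic fluid, 6: ascites; pleural, pericardial and retroperitoneal effusion; pelvic fluid collection; perinephric collection.
- Other organ oedema, 4: gastrointestinal, perinephric, retroperitoneal, visceral.

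5 + 4 + 6 + 4 = 19, and 19/42 = 45%. Setting aside cytotoxic oedema, whose wording names no organ, leaves 18. Two terms name a peripheral site: *Oedema peripheral* and *Peripheral swelling*. The remaining 42 − 19 − 2 = 21 are skin, systemic or unspecified.

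**The case against.** The strongest reply is that the documents already disclose the components and limit what enters the count. Most of its parts have force.

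- **Display.** SAP 4.6.2 tabulates safety-topic TEAEs by PT and lists every serious adverse event. Ketoacidosis, ketonuria and lactic acidosis will each be visible by arm, and any serious ketoacidosis case can be identified. A reader might infer that the 13-term list hides a true difference in ketoacidosis. The documents do not support that: the pooled row may blur a difference, but the PT rows still show it.
- **Entry filters.** Urinalysis, which includes ketones (Protocol 10.2), is scheduled at Visits 25 and 33, at early discontinuation and at Visit 802. A reader might infer that routine ketone results flow into the DKA count. They do not do so automatically. The SAP searches TEAEs only. Protocol 8.2.4 and 10.3.1 require clinical relevance or significance and exclude findings of the underlying disease unless worse than expected, and Protocol 10.3.4 prefers a diagnosis to its signs. These filters reduce frequency. They do not correct the classification of what passes through, and lactic acidosis is itself a diagnosis.
- **Search breadth.** A sensitive first-pass search is legitimate, and the retinopathy list in Appendix 6 is broad too. But 4.6.2.1.6 presents the result as participants who experienced DKA, not as a search yield.
- **Narrowing has a cost.** Replacing the list with the 4 ketoacidosis terms would lose an event coded only as diabetic ketosis because acidosis was not recorded. This stands, and is a reason to add a narrow row rather than drop the broad one.
- **Edema.** SAP 4.6.2.1.8 reports by PT and states no pooled headline figure. A pleural effusion would appear under its own name. This largely answers the edema half; what remains is the title of the set.

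**Conclusion.** The point holds for the pooled DKA figure. As written, the number and percentage in SAP 4.6.2.1.6 measure participants with any of 13 ketone-related or acidosis terms, 9 of which do not name ketoacidosis. They are not an incidence of DKA, and neither the by-PT rows nor the serious event listing supplies that incidence as a count of distinct participants.

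The size of the distortion is unknown. The range of 0.6% to 1.8% against 0.3% rests entirely on assumed counts (1 true case, 1 to 5 off-target participants, 335 per arm). A reader might take the 69% share of terms, or the four-fold ratio in one row of the illustration, as a forecast. Neither is: a listed term with no events adds nothing, and the documents give no event rates.

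For edema the conclusion is limited to labelling: 19 of 42 terms cannot properly sit under a peripheral heading, but the planned output is by PT.

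Both topics are safety summaries with no alpha or decision rule attached. No primary, gated or other secondary endpoint in SAP 1.1 depends on them.

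**What to change.** In SAP 4.6.2.1.6:

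1. Keep the broad search, but label the group *ketosis/ketoacidosis-related terms*. It holds 12 terms once lactic acidosis is moved out (4 + 2 + 6).
2. Add a row labelled *DKA* that counts distinct participants with any of the 4 ketoacidosis PTs.
3. Report lactic acidosis on its own row, outside the DKA group.

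If comparison with other studies needs the 13-term total, it can be retained under a neutral label.

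In SAP 4.6.2.1.8 and Appendix 7, rename the set *oedema, effusion and fluid-retention terms*. Any figure that still carries the name peripheral edema should exclude the organ and cavity terms. If such a figure is produced, list its terms in full, including a decision on unspecified entries such as *Oedema*, *Swelling*, *Fluid retention* and *Oedema due to cardiac disease*.

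The cost is a wording change, a regrouping of terms already coded and a few extra table rows. No new data are needed.

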#### 4.6.2.1.7. Diabetic Retinopathy or Maculopathy

The diabetic retinopathy or maculopathy will be searched by MedDRA PTs from all TEAEs. The list of PTs for the search is provided in Appendix 6 (Section 6.6). A summary of treatment-emergent retinopathy or maculopathy by PT will be provided.

